7.3. Sensitivity Analyses for Primary Efficacy Variable

The robustness of the primary analysis results will be explored by applying it, as described in the previous section, to the PP population as well. In addition the, following sensitivity analysis will be performed:

- Repeat of the primary analysis without introduction of covariates except for the treatment group, week and week by treatment interaction.
- Repeat the primary analysis when introducing additional baseline covariates variables that differ appreciably between the laquinimod 0.6 mg and placebo treatment groups, if any, i.e. $p\text{-value} \leq 0.05$. The additional baseline covariates are:
 - Gender,
 - Age at baseline,
 - Time from first MS symptom (years),
 - Time from PPMS diagnosis (years),
 - Proportion of patients with GdE at baseline,
 - Proportion of patients whose PPMS diagnostic criteria includes positive CSF,
 - Proportion of patients with baseline EDSS ≤ 4.5 vs > 4.5 .

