**Table 1: ALLEGRO: Summary of Efficacy Results**

Endpoints	% reduction (p-value)
ARR	23% (0.0024)
EDSS progression (3m confirmation)	36% (0.0122)
EDSS progression (6m confirmation)a	48% (0.0023)
Cumulative number of GdE T1 lesions	37% (0.0003)
Cumulative number of new T2 lesions	30% (0.0002)
Brain Atrophya	32.8% a (< 0.0001)
MSFC z-score	51% (0.59)

a Post Hoc analysis

ARR = annualized relapse rate, EDSS = Expanded Disability Status Scale, GdE = gadolinium enhancing, MSFC = Multiple Sclerosis Functional Composite

Overall, the BRAVO study did not meet its primary endpoint (ARR; 17.7% reduction, p=0.0746), and some explanations for this result are proposed based on lack of power to detect the observed effect and post-hoc analyses showing baseline MRI imbalance in favor of the placebo group. It is Teva's assessment that the results obtained after a covariate analysis correcting for these baseline imbalances (ARR; 21.3%, p=0.0264) represent the true effect of laquinimod 0.6 mg in this patient population (Table 2).

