### 6.4.1. MRI Evaluations

The patients will undergo up to 3 MRI scans:

- baseline (at least 14 days but not more than 6 weeks prior to baseline)
- week 24
- week 48 (or ET visit if performed after the week 36 visit and prior to week 48).

Gd will be administered at baseline MRI only. In case of steroid treatment, study MRI should be performed before or be delayed to allow a minimum of 14 days, but not more than 28 days, from the completion of the steroid course.

The following parameters will be assessed:

- normalized brain volume - at baseline
- PBVC – at week 24 as well as week 48 or ET
- T2-lesions volume – at baseline, as well as week 48 or ET
- T1 hypointense lesions volume - at baseline, as well as week 48 or ET
- number of GdE-T1 lesions – at baseline
- number of new T2 lesions - at week 48 or ET
- number of new T1 hypointense lesions - at week 48 or ET
- thalamic volume, cortical volume, and white matter volume - at baseline
- percent volume change (thalamus, cortex, white matter) - at week 48 or ET
- normalized cervical cord area based on 3D T1-w acquisition of the cervical cord - at baseline
- cervical cord area percentage volume change - at week 48 or ET
- number of T2 cervical cord lesions based on a sagittal T2 acquisition of the cervical cord - at baseline
- number of new T2 cervical cord lesions based on a sagittal T2 acquisition of the cervical cord - at week 48 or ET
- normal-appearing brain tissue average MTR, at baseline, as well as week 48 or ET

If MTR is not performed due to MRI site technical limitations, this would not be considered a protocol violation.

Additional details of MRI procedures are presented in [Appendix F](#) and in the MRI manual.

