#### **9.6.4.2. Sensitivity Analyses**

The robustness of the primary analysis results will be explored by applying it, as described in the previous section, to the PP population as well. In addition the, following sensitivity analysis will be performed:

- Repeat the primary analysis without introduction of covariates except for the treatment group, week, and treatment by week interaction.
- Repeat the primary analysis when introducing additional baseline covariates variables that differ appreciably between the treatment groups, if any. The list of baseline measurements will be provided in the SAP.

- Repeat the primary analysis while including observations that were recorded following an early termination visit.

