6.3. Demographics and Baseline Characteristics

Demographics and baseline characteristics will be presented for the following populations: ITT, mITT1, patients who performed an ET visit during part A of the study, patients who completed part A of the study, patients who performed an ET visit during part B of the study, patients who completed part B of the study.

Patient demographics and baseline characteristics will be examined to assess the comparability of the treatment groups. The continuous variables of patient age, weight, height, and body mass index (BMI), will be summarized using descriptive statistics. The categorical variables of patient sex, race and ethnicity will be summarized using descriptive statistics for each category. Missing categories will be presented if necessary.

Baseline PPMS characteristics will be presented in a separate table. Continuous variables of time from 1st MS symptom (years) to informed consent, time from PPMS diagnosis (years) to informed consent, EDSS will be summarized using descriptive statistics. The categorical variables of previous use of disease modifying treatments, combination of tests used to meet PPMS criteria (at least two), patients with positive CSF, areas with evidence of clinical disability progression in the 2 years prior to screening, EDSS raw score and EDSS score defined as ≤ 4.5 and >4.5 will be summarized using descriptive statistics for each category. Missing categories will be presented if necessary.

Baseline MRI measurements will be presented in a separate table as well. Continuous variables of normalized brain volume, T2 lesion volume, and number of T1 enhancing lesions will be summarized using descriptive statistics. The categorical variable of patients with T1 enhancing lesions at baseline will be summarized using descriptive statistics for each category

Tobacco usage will also be summarized using descriptive statistics.

The following statistical tests will be incorporated for baseline tabulations between 0.6mg and placebo:

- Analysis of variance (ANOVA) with treatment group and CGR as factors will be used for all continuous variables presented for demography, PPMS history and normalized brain volume.
- Wilcoxon-Mann-Whitney test will be used for EDSS and for T2 lesion volume.
- Cochran-Mantel-Haenszel (CMH) test, stratified by CGR will be used for all categorical variables.

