When the study is completed, actual values of T25FW and changes from baseline to each visit will be summarized using descriptive statistics to include both part A and part B. Also, the changes from baseline to each visit will be analyzed using similar statistical methodology as presented in this section for changes from baseline to week 48 in T25FW test.

7.4.4. The number of new T2 lesions at week 48

The number of new T2 lesions at week 48 compared to baseline will be analyzed using the mITT1 population and will include all the assessments done up to one month after the last dose of the study drug (all the following assessments will be excluded from this analysis). This analysis will be performed using baseline adjusted negative binomial regression model (SAS® PROC GENMOD) in which 1 contrast for comparing laquinimod 0.6 mg to placebo will be constructed. In addition to the treatment group, the natural logarithm of T2 lesion volume at baseline, age at baseline and CGR will be used as covariates. The SAS code for this analysis is as follows:

```
PROC GENMOD;
  CLASS ARM CGR;
  MODEL T2LES=ARM LT2BASE AGE CGR/ DIST=NB LINK=LOG TYPE3;
```

```
LSMEANS ARM/ CL;  
ESTIMATE 'Laq 0.6 to Plb' ARM 1 -1 / ESTIMATE=EXP;  
WHERE ARM in ('Laquinimod 0.6 mg', 'Placebo');  
RUN;
```

In addition, the number of new T2 lesions at week 48 will be summarized using descriptive statistics.

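### The adjusted PBVC sensitivity model admits its seven listed covariates only on a baseline difference at p ≤ 0.05, so it most likely repeats the primary analysis

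*SAP*

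**What the plan says.** Protocol 9.6.4.2 calls for a repeat of the primary analysis with "baseline covariates variables that differ appreciably between the treatment groups, if any". It sets no threshold and leaves the list to the SAP.

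SAP 7.3 supplies both: "Repeat the primary analysis when introducing additional baseline covariates variables that differ appreciably between the laquinimod 0.6 mg and placebo treatment groups", with p ≤ 0.05 as the criterion, and seven candidates. These are gender, age, time from first MS symptom, time from PPMS diagnosis, "Proportion of patients with GdE at baseline", positive CSF among the diagnostic criteria, and EDSS ≤4.5 versus >4.5.

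The baseline comparisons are in SAP 6.3: "Analysis of variance (ANOVA) with treatment group and CGR as factors will be used for all continuous variables" in demography, PPMS history and normalised brain volume, and a CMH test stratified by country/region for categorical variables. Baseline tables are planned for the ITT and mITT1 sets, among others. SAP 7.3 does not say which set supplies the deciding p-value.

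The primary model (SAP 7.2) always contains normalised brain volume, log T2 lesion volume and country/region, and none of the seven.

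Baseline enhancement is collected in this trial: Protocol 6.4.1 lists "number of GdE-T1 lesions" at baseline. The new-T2 model in SAP 7.4.4 does not use it: "MODEL T2LES=ARM LT2BASE AGE CGR/ DIST=NB LINK=LOG TYPE3". The by-gender version in SAP 7.5.21 adds only gender terms.

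**The concern.** Allocation between 0.6 mg and placebo is random, 1:1 in both enrolment periods. A baseline p-value therefore shows how far chance has separated the arms on a variable. It carries no information on whether that variable relates to brain-volume change. Under the rule a variable closely related to PBVC is left out at p = 0.10, while an unrelated one enters at p = 0.04.

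Two consequences follow. The run will usually contain no added covariate and so show nothing beyond the primary result. When it does contain one, the final model cannot be written down until the arms are compared.

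SAP Section 12 also removes the sensitivity analyses that used data after early termination. For PBVC, SAP 7.3 keeps a per-protocol rerun, an unadjusted rerun and this run, which is the only one of the three meant to add covariates.

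**Working it through.** **Plan's own figure.** Inputs from Protocol 9.2: difference 0.3, SD 0.8, two-sided 5%, 126 evaluable per arm.
- 0.3 / (0.8 × √(2/126)) = 2.976, and 2.976 − 1.96 = 1.016. The normal probability is 84.5% (84.3% with the noncentral t), against 84% stated.
- 252 / 0.9 = 280. Both figures reproduce, so 126 per arm is used below.

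**Chance that no covariate enters.** Seven tests, each at 5% under randomisation.
- Independent tests: 0.95^7 = 0.698. Exactly one enters: 7 × 0.05 × 0.95^6 = 0.257. Two or more: 1 − 0.698 − 0.257 = 0.045 (0.044 before rounding).
- At least one enters: 1 − 0.698 = 0.302. Expected number entering: 7 × 0.05 = 0.35.
- Lower bound under any dependence: 1 − 7 × 0.05 = 0.65.
- Simulation, 20,000 trials per setting with 126 per arm, with an assumed correlation among age, the two disease durations and EDSS: 0.699, 0.700, 0.721 and 0.740 for correlations of 0, 0.3, 0.5 and 0.7. It used simple two-sample tests, not the region-adjusted ones.

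**Imbalance needed to enter.**
- Continuous: 1.96 × √(2/126) = 0.25 SD.
- Binary: 1.96 × √(2p(1 − p)/126), which is 7.4 percentage points at an assumed prevalence of 10% and 12.3 points at 50%.
- Smaller imbalances stay unadjusted, whatever the variable's relation to outcome.

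**What a fixed set could add.** The documents give no R² for these covariates. If they explained an assumed 5%, 10% or 20% of residual PBVC variance, the SD would shrink by √(1 − R²). Power at 126 per arm would go from 84.5% to 86.3%, 88.1% or 91.4%. With R² near zero there would be no gain.

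**New-T2 model.** No calculation is possible: the documents give neither the prevalence of enhancement in this population nor its association with new T2 lesions.

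**The case against.** The run has a narrow purpose: to check covariates that turn out unbalanced, if any. Agreement with the primary analysis when nothing differs is then the intended result. The list, threshold and tests are prespecified and use baseline data only, so the rule cannot bias the randomised comparison. The run also lies outside the hierarchy in SAP 5.3. Other covariate checks always run: the unadjusted repeat (SAP 7.3), the treatment-by-covariate and treatment-by-region models (SAP 7.2) and the by-gender PBVC model (SAP 7.5.21). All of this stands. It lowers the importance of the point, but it does not make a baseline p-value a good way to choose covariates.

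A reader might infer more from the sponsor's RRMS trial BRAVO, where Protocol 1.3.2.2 cites "post-hoc analyses showing baseline MRI imbalance in favor of the placebo group". In Protocol Table 2 the correction moved new T2 lesions from 16.5% (p=0.08) to 18.7% (p=0.037). That does not show what is at stake here. The rule in SAP 7.3 concerns PBVC, and the brain-atrophy row of the same table hardly moved: 27.6% (p=0.0001) to 27.4% (p<0.0001). The footnote in Protocol 1.4.1 mentions two corrected MRI parameters without naming them, so enhancement cannot be credited. New T2 lesions were an exploratory endpoint there, and the population was relapsing.

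A reader might also take the seven covariates to be established predictors. The documents never call them prognostic.

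**Conclusion.** The point holds as a modest improvement. Under randomisation the adjusted run duplicates the primary analysis in about 70% of trials: 65% at the least, and 70% to 74% under the assumed correlations. In the remaining 30% or so, chance imbalance selects its model. This assumes that each baseline test holds its 5% level.

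Neither the PBVC model nor the new-T2 model is an error, and the documents do not support a claim of bias. Normalised brain volume, log T2 volume and country/region are adjusted for unconditionally in the primary model, and age is already in the new-T2 model. Any gain in precision depends on associations that the documents do not report. For the new-T2 model, the last of four endpoints in the hierarchy, adding enhancement is reasonable but unquantified.

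**What to change.** In SAP 7.3, delete the p ≤ 0.05 rule and state that the primary model is refitted with all seven listed covariates whatever their baseline comparison. Code CSF as documented positive versus not: under Protocol Appendix D two of three criteria suffice, so a patient without positive CSF may be untested and not negative. Deleting the rule also removes the question of which analysis set decides entry. Record the departure from Protocol 9.6.4.2 in SAP Section 12, before unblinding.

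As a secondary change, add baseline enhancement (yes/no) to the negative binomial model in SAP 7.4.4, or specify a named sensitivity version that contains it.

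Cost: a few SAP sentences, about seven degrees of freedom among about 250 patients for PBVC, and one in the new-T2 model. SAP 5.5 leaves a wholly missing MS date missing, so those patients drop from the adjusted PBVC run. Patients without a post-gadolinium baseline scan drop from any model containing enhancement. Report how many patients contribute. Age and the two durations may overlap, so their separate coefficients should not be interpreted. For that potential loss of patients, the named sensitivity version is the more cautious choice for new T2 lesions.

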7.4. Secondary Efficacy Variables and Analysis

7.4.1. Time to CDP as measured by EDSS.

Time to CDP will be defined as increase in EDSS of ≥ 1 point from baseline EDSS, if EDSS at entry is ≤ 5.0 or increase of ≥ 0.5 point, if EDSS at entry is ≥ 5.5 . This increase should be confirmed after at least 12 weeks. Progression cannot be confirmed during a protocol defined relapse.

To calculate the time of CDP, the following algorithm will be used:

Let E_t be an EDSS measurement of the patient under consideration observed at time (measured by weeks from the patient's baseline date).

Let E_0 be the baseline EDSS measurement for that patient.

Let $s = t + 12$.

The time to CDP for the patient under consideration is defined as t if all the following conditions hold:

1. If $0 \leq E_0 \leq 5$ then let $\Delta = 1$. Otherwise, let $\Delta = 0.5$.
2. $E_t \geq E_0 + \Delta$.
3. For any $t < q_1 < s$, if the patient's EDSS was evaluated at time q_1 , then $E_{q_1} \geq E_0 + \Delta$
4. $E_{q_2} \geq E_0 + \Delta$ for some $q_2 \geq s$, and at time q_2 , the patient was not experiencing a relapse (i.e. q_2 is not between onset and stabilization date of a relapse).
5. t is the earliest time point during the study in which conditions 2-4 hold.

If no such t exists, then the time to confirmed progression will be right censored by the patient's last EDSS evaluation date from Part A (or part B if the data from both part A and part B is used for analysis) of the study. In case time t exists without fulfilling conditions 3 and 4 because time q_2 is after the patient completed Part A (or part B if the data from both part A and part B is used for analysis) of the study (or performed ET), and therefore cannot be seen, then the right censored will be on time t and not in the last EDSS evaluation.

If a patient died due to MS disease progression, then this patient will be analyzed as having CDP and the time to CDP will be calculated using the onset date of progression.

If a patient died due to MS before having progression, then the time to disability progression will be censored using the date of death.

Time to CDP as measured by EDSS confirmed after at least 12 weeks will be analyzed using the ITT population and will include data from all the study assessments done up to seven days after the last dose of the study drug (all the following assessments will be excluded from this analysis). This analysis will be performed using a baseline adjusted Cox's proportional hazards regression model (SAS® PROC PHREG) in which 1 contrast for comparing laquinimod 0.6 mg to placebo will be constructed. In addition to treatment group, categorical EDSS at baseline (≤ 4.5 or > 4.5), age at baseline, natural logarithm of T2 lesion volume at baseline, and CGR will be used as covariates. The SAS code for this analysis is as follows:

```

PROC PHREG;
  CLASS ARM EDSSBASE CGR;
  MODEL TIME_TO_PROGRESSION*CENSOR(1,2,3)=ARM EDSSBASE AGE LT2BASE CGR / COVB RL;
  CONTRAST 'Laq 0.6 to Plb' ARM 1 / ESTIMATE=EXP;
  WHERE ARM in ('Laquinimod 0.6 mg', 'Placebo');
RUN;

```

In case the above model will not converge due to CGR variable, then CGR will be removed from the model.

The adequacy of the proportional hazards assumption will be confirmed by including a time-dependent covariate of laquinimod 0.6 mg (as dummy variables) by log (time) interaction in the analysis model and testing it at the 5% level. In case the proportional hazards assumption will

be rejected, the log rank test (SAS® PROC LIFTEST) will be used for statistical inference. The SAS code for checking the proportional hazards assumption is as follows:

```
PROC PHREG;
  CLASS ARM EDSSBASE CGR;
  MODEL TIME_TO_PROGRESSION*CENSOR(1,2,3)=ARM ARMT EDSSBASE AGE LT2BASE CGR ;
    ARMT = ARM*log(TIME_TO_PROGRESSION);
    PROP_HAZARDS_TEST_LAQ_0_6: test ARMT;
    WHERE ARM in ('Laquinimod 0.6 mg', 'Placebo');
  RUN;
```

In case the above model will not converge due to CGR variable, then CGR will be removed from the model.

In addition, patients with CDP will be summarized using descriptive statistics. The time to CDP will be presented by Kaplan-Meier curves stratified by treatment group.

EDSS scores and changes from baseline to each visit will be summarized using descriptive statistics.

All analyses presented in the section will be repeated to include both part A and part B when the study is completed.

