- All patients will undergo brain and cervical spinal cord MRI scans at week 0 (without and with Gd), week 24 (without Gd), and week 48 (without Gd). ET visit will include MRI for patients who prematurely terminate treatment subsequent to the week 36 visit and prior to week 48.
- EDSS and FSS will be performed at screening, week 0, and every 12 weeks until completion/ET, if applicable.
- Timed 25-foot walk (T25FW), 9-Hole Peg test (9HPT), and symbol digit modalities test (SDMT) will be performed at week 0, and every 12 weeks until completion/ET, if applicable. At weeks 0, 48, and every 48 weeks thereafter, SDMT will be performed as part of the Brief International Cognitive Assessment for Multiple Sclerosis (BICAMS) assessment.
- BICAMS, including SDMT, will be evaluated at weeks 0, 48, and every 48 weeks thereafter.
- Low contrast visual acuity (LCVA) will be assessed at weeks 0 and 24 and every 24 weeks until completion/ET, if applicable.
- Walking ability will be assessed by the 12-Item Multiple Sclerosis Walking Scale (MSWS-12) at weeks 0 and 12 and every 12 weeks until completion/ET.
- Ancillary studies:
  - Cerebrospinal fluid (CSF) (to be performed in selected sites) will be collected from all patients who signed an appropriate, Ethic Committee (EC) approved informed consent form, at week 48.
  - Optical coherence tomography (OCT) evaluation (to be performed in selected sites) will be performed in all patients who signed an appropriate, EC approved informed consent form, at weeks 0, 48, and 96 to assess retinal thickness.

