      - anemia panel (blood smear, serum iron, ferritin, total iron binding capacity, folic acid, haptoglobin, IL-1, IL-6, IFN- $\gamma$ , TNF- $\alpha$ , and hepcidin) and B12

- additional investigations and follow-up per the investigator's discretion or sponsor's request
- Serum chemistry (including electrolytes, fibrinogen, glucose, urea, creatinine, liver enzymes, CPK, CRP, pancreatic amylase, total protein, albumin, direct and total bilirubin).
- estimated GFR\*
- Fasting lipid profile at week 48 and every 48 weeks until completion/ET.
- Serum TSH, T3, and free T4 at week 24 and every 24 weeks until completion/ET.
- Blood samples for potential biomarker measures will be collected at weeks 24 and 48.
- Pharmacokinetic study: blood samples for analysis of laquinimod plasma concentrations will be collected at weeks 4, 8, 12, 24 and 48.\*
- Ascertain use of acceptable contraception.\*
- All patients will undergo brain and cervical spinal cord MRI scans without Gd at weeks 24 and 48.
  - Weeks 24 and 48 MRI will be performed within 14 days of the clinical visit.
  - In case of steroid treatment, study MRI should be performed before such treatment or delayed to allow a minimum of 14 days but not more than 28 days from the completion of the steroid course.
- EDSS and FSS will be performed every 12 weeks until completion/ET visit (if applicable)
- T25FW, 9HPT, and SDMT will be performed every 12 weeks until completion/ET visit (if applicable). At week 48 and every 48 weeks thereafter, SDMT will be performed as part of the BICAMS assessment.
- mRS will be evaluated at week 72.
- BICAMS, including SDMT, will be evaluated at week 48 every 48 weeks thereafter.
- LCVA will be assessed at week 24 and every 24 weeks until completion/ET.
- MSWS-12 will be performed at week 12 and every 12 weeks until completion/ET.
- Evaluation and management of major modifiable cardiac risk factors (with referral to treatment and follow-up in suitable clinic if needed) will be performed at weeks 96 and 144.
- Ancillary studies:
  - CSF (to be performed in selected sites) will be collected from all patients who signed an appropriate, EC approved informed consent form, at week 48 (see Section 8.4.1 for further details of the assessments).

- OCT evaluation (to be performed in selected sites) will be performed in all patients who signed an appropriate, EC approved informed consent form, at weeks 48 and 96 to assess retinal thickness.

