### 9.6.2. Secondary Variables

#### 1. Time to CDP.

Time to CDP will be defined as increase in EDSS of  $\geq 1$  point from baseline EDSS, if EDSS at entry is  $\leq 5.0$  or increase of  $\geq 0.5$  point, if EDSS at entry is  $\geq 5.5$ . This increase should be confirmed after at least 12 weeks. Progression cannot be confirmed during a relapse.

To calculate the time of CDP, the following algorithm will be used:

Let  $E_t$  be an EDSS measurement of the patient under consideration observed at time (measured by weeks from the patient's baseline date).

Let  $E_0$  be the baseline EDSS measurement for that patient.

Let  $s = t + 12$ .

The time to CDP for the patient under consideration is defined as  $t$  if all the following conditions hold:

1. If  $0 \leq E_0 \leq 5$  then let  $\Delta = 1$ . Otherwise, let  $\Delta = 0.5$ .
2.  $E_t \geq E_0 + \Delta$ .
3. For any  $t < q_1 < s$ , if the patient's EDSS was evaluated at time  $q_1$ , then  $E_{q_1} \geq E_0 + \Delta$
4.  $E_{q_2} \geq E_0 + \Delta$  for some  $q_2 \geq s$ , and at time  $q_2$ , the patient was not experiencing a relapse.
5.  $t$  is the earliest time point during the study in which conditions 2-4 hold.

If no such  $t$  exists, then the time to confirmed progression will be right censored by the patient's last EDSS evaluation date from Part A of the study. In case time  $t$  exists without fulfilling conditions 3 and 4 because time  $q_2$  is after the patient completed Part A of the study (or performed ET), and therefore cannot be seen, then the right censored will be on time  $t$  and not in the last EDSS evaluation.

If a patient died due to MS disease progression, then this patient will be analyzed as having CDP and the time to CDP will be calculated using the onset date of progression.

If a patient died due to MS before having progression, then the time to disability progression will be censored using the date of death.

2. Time to CDP event defined by reaching at least 1 of the following 2 types of event for each individual:
  - An increase from baseline in EDSS score ( $\geq 1$  point from baseline EDSS, if EDSS at entry is  $\leq 5.0$  or increase of  $\geq 0.5$  point, if EDSS at entry is  $\geq 5.5$ ), confirmed after at least 12 weeks, **or**
  - An increase of at least 20% from baseline in the T25FW score, confirmed after at least 12 weeks

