First dose at site		X									
Adverse event	X	X	X	X	X	X	X	X	X		
Physical examination	X	X	X	X	X	X	X	X	X		
Vital signs ^d	X	X ^d	X	X	X	X	X	X	X		
ECG	X	X ^e	X	X	X	X		X	X		
Chest X-ray ^f	X										
Anemia panel ^g		X	Anemia panel is performed if there is a confirmed hemoglobin decrease of >1 g/dL from baseline								
B12	X		B12 is analyzed if there is a confirmed hemoglobin decrease of >1 g/dL from baseline								
Safety laboratory tests ^h	X	X	X	X	X	X	X	X	X		
Fasting lipid profile ^j		X						X	X		
Thyroid function tests		X				X		X	X		
GFR ^k	X	X	X	X	X	X	X	X	X	X ⁱ	
HTLV- I/II	X										
Urinalysis	X										
β-hCG ^l	X	X	X	X	X	X	X	X	X		
Home urine β-hCG test ^m					Every 28±2 days between visits; telephone confirmation within 72 hours of the scheduled home pregnancy test						
Ascertain use of acceptable contraception	X	X	X	X	X	X	X	X	X		
Call IVRS/IWRS	X	X	X	X	X	X	X	X	X		

Visit	Screening	Baseline	1	2	3	4	5	6	ET	Unscheduled Visit ^a
Study week^b	up to -6	0	4	8	12	24	36	48		
Study drug dispensing		X	X	X	X	X	X	X		
Study drug accountability			X	X	X	X	X	X	X	
MRI ^c		X				X		X	X ⁿ	
EDSS/FSS ^d	X	X			X	X	X	X	X	
T25FW ^p		X			X	X	X	X	X	
9HPT ^p		X			X	X	X	X	X	
SDMT ^{p,q}		X ^q			X	X	X	X ^q	X	
BICAMS ^{p,q}		X						X	X ^r	
LCVA		X				X		X	X	
MSWS-12		X			X	X	X	X	X	
Pharmacokinetic samples			X	X	X	X		X		X ⁱ
Potential biomarker samples		X				X		X		X ⁱ
Pharmacogenomic sample ^s		X								
Ancillary studies										
CSF assessment ^t								X		
OCT evaluation		X ^u						X	X ^v	

Patients who are discontinued from study treatment will be encouraged to continue all scheduled visits and procedures after study drug discontinuation (with the exception of procedures associated with drug dispensing and accountability, pregnancy testing, and pharmacokinetic sampling).

^a An unscheduled visit may be performed at any time at the patient's request or per investigator's discretion. Only mandatory procedures are specified; additional assessments per clinical discretion. In addition, unscheduled urgent safety laboratory samples, pharmacokinetic blood samples, and/or samples for potential biomarker analyses may be collected at the discretion of the investigator or medical monitor at any time to assist with further investigations of cardiovascular events or other clinical event of interest. The samples should be collected as soon as possible in association with the event.

^b For the purpose of scheduling study visits, a week is defined as 7±2 days.

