5.6. Study days and visit windows

Study days will be numbered relative to the 1st day of study drug administration. The start of treatment (day 1) is defined as the date on which a patient takes the 1st dose of study drug. Days will be numbered relative to study start (i.e., ..., -2, -1, 1, 2, ...; with day 1 being the start of study drug and day -1 being the day before the start of study drug). No windows schemes will be applied to the data.

For by-visit summaries, if there are multiple assessments at a post baseline time point then the last non-missing assessment at that visit will be used for the summary.

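### The 12-week confirmation rule for disability progression leaves no slack against 12-weekly EDSS visits that may fall two days early

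*SAP*

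**What the plan says.** SAP 7.4.1 defines progression by a rise in EDSS and adds: "This increase should be confirmed after at least 12 weeks". In the algorithm, onset is at time t, s = t + 12, and time is "measured by weeks from the patient's baseline date" (Protocol 9.6.2; the SAP uses the same words).

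- **Condition 3:** any EDSS taken strictly between t and s must also show the increase.
- **Condition 4:** some visit q2 at or after s must show it, outside a relapse.
- **Condition 5:** "t is the earliest time point during the study in which conditions 2-4 hold".
- **Censoring:** if q2 would fall after the end of Part A or after early termination, the patient is censored at t.

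On timing, the Protocol synopsis says: "EDSS and FSS will be performed at screening, week 0, and every 12 weeks until completion/ET, if applicable". SAP Table 1, note b, says: "For the purpose of scheduling study visits, a week is defined as 7±2 days". SAP 5.6 says: "No windows schemes will be applied to the data". Part A guarantees 48 weeks, and the analysis stops seven days after the last dose.

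The algorithm carries over to the EDSS-or-T25FW composite (7.4.2), the four-component composite (7.5.3) and T25FW alone (7.5.20). Section 7.5.4 uses it with 24 weeks. SAP 5.3 places the EDSS endpoint and the EDSS-or-T25FW composite first and second in the secondary hierarchy.

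**The concern.** The scheduled gap between EDSS visits equals the minimum gap for confirmation exactly. A visit one or two days early, which the schedule permits, can therefore fall short of s. Suppose a patient is worse at week 24 and still worse at a week 36 visit 83 days later. On dates, that visit satisfies condition 3 but cannot satisfy condition 4, and the patient needs a third progressed visit about 24 weeks after onset. If treatment or Part A ends first, the patient is censored at t.

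At stake are event counts and precision for the first two secondary endpoints. Whether a patient needs 12 or about 24 weeks of confirmation would turn on a day or two of scheduling. The text also does not say how weeks are computed, so two programmers could derive different event sets.

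**Working it through.** **Inputs from the documents:** required gap 12 × 7 = 84 days; nominal gap 84 days; tolerance read as ±2 days per visit; no analysis window; four post-baseline EDSS visits in 48 weeks.

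**Assumed:** how actual visit days spread within the tolerance. The documents do not say. They also give no event count, power or rate of missed confirmation for this endpoint, so there is no planned figure to reproduce.

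**Step 1: possible gaps.** With day offsets d1 (onset visit) and d2 (next visit), both scheduled from baseline, the gap is 84 + d2 − d1, which runs from 80 to 88 days. The next visit is too early when d2 < d1.

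**Step 2: how often.** With five equally likely days there are 25 pairs. Five are ties and the other 20 split evenly, so 10/25 = 40%. If the next visit is scheduled from the previous one instead, it fails for offsets −1 and −2: 2/5 = 40%. In general, for baseline-scheduled visits, P(too early) = (1 − P(tie))/2. With half of visits on the exact day and the rest spread evenly, P(tie) = 0.5² + 4 × 0.125² = 0.3125, giving 34%.

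**Step 3: effect on events.** If two later visits exist, the second is at least 168 − 4 = 164 days after onset. A sustained progression is then confirmed with t unchanged. It is lost only if exactly one later visit exists and that visit is early. With K post-baseline visits and onset equally likely at each of the K − 1 confirmable ones (assumption), the share lost is P(too early)/(K − 1), for example 0.40/3 = 13%.

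| Visits on exact day | Next visit too early | Lost, K = 4 | Lost, K = 6 | Lost, K = 8 |
|---|---|---|---|---|
| 20% (equal days) | 40% | 13% | 8% | 6% |
| 50% | 34% | 11% | 7% | 5% |
| 70% | 24% | 8% | 5% | 3% |
| 90% | 9% | 3% | 2% | 1% |

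**Step 4: other readings of the weeks.** Rounded to whole weeks, or taken as nominal visit weeks, the gap is always 12 and nothing fails. If the tolerance is multiplied out as 12 × (7 ± 2) = 84 ± 24 days, 49% fail.

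**Step 5: simulation.** This assumes 6% onset per visit and independent offsets, and compares 84-day with 80-day minimum gaps. Equal days without reversion gives losses of 13%, 7% and 5% for K = 4, 6 and 8. If 20% of elevated scores revert at each visit, the losses are 18%, 14% and 12%. With reversion and 90% of visits on the exact day they are 4%, 3% and 3%.

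**Step 6: size of the repair.** A minimum of 82 days still fails when d2 − d1 is −3 or −4: 3/25 = 12%. A minimum of 80 days (84 − 2 − 2) fails none. For 24 weeks the matching figure is 168 − 4 = 164 days.

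**The case against.** The best counter-argument is that exact-day arithmetic is only one reading. The algorithm measures time in weeks and the schedule labels visits by week, so week 24 followed by week 36 could be meant to confirm. The no-windows statement may mean only that visits are not reassigned by study day. This stands as a possibility, and it puts the lower end of the range at zero. But the SAP does not state it, and it dates time from baseline and censors at an evaluation date, which points towards actual dates.

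Three further points stand:

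- **The early visit is not discarded.** A reader might infer that it does not count at all. It counts under condition 3, and any later qualifying visit confirms with the same t.
- **Losses are partly recoverable.** SAP 7.4.1 and 7.4.2 repeat these analyses with Part B data, where 12-weekly visits continue, although that repeat is exploratory.
- **Four visits is the short end.** Of 286 patients randomised before 2016, 95 went to 1.5 mg, so 191 of the planned 280 on 0.6 mg or placebo were already in. Enrolment stood at 301 of 375 on 1 February 2016. Exactly 48 weeks of follow-up therefore describes mainly late enrollees.

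**Conclusion.** The point holds as a gap in the derivation rule. The minimum confirmation interval equals the visit interval, early visits are allowed, and nothing absorbs the difference. Read on dates, some patients with two consecutive progressed visits are censored at t.

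Its size rests on an assumption about punctuality. Too-early next visits run from 40% (equal days) through 24–34% (50–70% of visits on the exact day) to 9% (90% on the day), and to 0% if weeks are rounded or nominal. Sustained progressions lost are about 13% with four visits and 5–8% with six to eight under equal days, falling to about 3% and 1–2% with 90% on the day.

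The documents do not support three stronger conclusions that a reader might draw:

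- They do not show that 40% of confirmations fail. That figure needs equally likely days and unrounded weeks.
- The 12-week label is not false. Confirmation at 24 weeks still satisfies a rule of at least 12.
- Nothing indicates bias between arms. The cost is lost events and precision.

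**What to change.** Before unblinding, state in SAP 7.4.1 that the confirmation interval is computed from actual visit dates, and set the minimum at 80 days: 84 less two days at each of the two visits. Carry this to 7.4.2, 7.5.3 and 7.5.20, and use 164 days in 7.5.4. Subtracting a single two-day tolerance is not enough, as step 6 shows.

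A limit in days is safer than nominal visits. SAP 5.5 treats an early termination visit as the next scheduled one for EDSS and T25FW, so a nominal rule could let a visit soon after onset pass as 12-week confirmation.

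List the change in SAP section 12, because it departs from Protocol 9.6.2, and keep the strict 84- and 168-day rules as a sensitivity analysis. The cost is a sentence of text and one constant in the derivation program (with its 24-week counterpart). The downside is that a few confirmations rest on 80 to 83 days (164 to 167 for the 24-week version).
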